## **13. EFFICACY ANALYSIS**

### **13.1. Primary Efficacy Variable Analyses**

The primary efficacy variable is the percentage of subjects who are GH responders on Day 14. GH response is defined as having a mean GH  $\leq 2.5 \mu\text{g/l}$  at Visit 8 (Day 14, after 6-day titration plus 8-day treatment with BIM23B065) or at least a 50% reduction in the mean GH change from baseline on Day 14. The mean serum concentration of GH is calculated at baseline and on Day 14 from the non-missing serum concentrations of GH recorded over 6 hours on these days. The number and proportion (%) of GH responders will be reported with its 90% confidence interval calculated using the exact Clopper-Pearson method. The null hypothesis that the GH responder rate is not clinically relevant (i.e.  $\leq 33\%$ ) will be tested at the one-sided 5% significance level. The exact p-value will be reported. The test will be rejected if the lower 90% confidence limit is larger than 33%. Primary efficacy analysis will be based on the Efficacy Evaluable population.

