### 5.2.1. Primary Endpoints and Evaluations

- The proportion of subjects with GH  $\leq 2.5\mu\text{g/l}$  or  $>50\%$  reduction from mean baseline GH (measured over 6 hours on Day -1) after 6-day titration plus 8-day treatment with BIM23B065 measured by mean serum concentration of GH over 6-hours on Day 14.

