## 6. STUDY METHODS

### 6.1. Overall Study Design and Plan

This is an open-label, non-randomised, multi-centre, adaptive two-stage phase II study.

During Stage 1, up to 12 subjects will be enrolled to receive BIM23B065 BID for two weeks. The primary endpoint will be the proportion of subjects with GH  $\leq 2.5$   $\mu\text{g/l}$  or  $>50\%$  reduction from baseline GH on Day 14. The mean serum concentration of GH collected over 6 hours will be used for the baseline (Day -1) and endpoint (Day 14) GH determination.

Several sequential analyses will occur during Stage 1. The Stage 1 arm (BID administration) may be terminated early for futility during each of these interim analyses if the responder rate does not exceed the pre-determined minimum efficacy criteria. In that case, a Stage 2 arm will be initiated during which up to 12 subjects will be recruited to receive BIM23B065 three times a day (TID) for 14 days. The same sequential analysis and early termination rule for futility will apply during Stage 2 as for Stage 1.

Any subjects who withdraw prior to the Day 14 end of treatment visit may be replaced except for early withdrawal due to safety and tolerability reasons. As soon as 12 subjects (out of which at least 8 are Octreotide responders as tested during the screening period) reach Visit 8, withdrawn subjects will not be replaced.

Both the BID and TID regimen parts will consist of 3 periods (See Figure 1):

- A screening period of 21 days maximum during which the eligibility criteria will be assessed. An Octreotide test will be also performed at the latest 7 days prior to first IMP administration.
- A treatment period that will consist of twice or three times daily administrations of BIM23B065. This period will last for 14 days. The first 6 days will be a titration of BIM23B065 (0.4 mg/0.6 mg/0.8 mg BID or TID). Then a stable target dose (1.0 mg) of BIM23B065 will be BID or TID administered from Day 7 to Day 14.
- If during the study, a subject experiences any safety or laboratory events (for detailed description see Table 1 of the Protocol), they may have their dose reduced to the prior dose. The minimum dose allowed for the treatment period is 0.6mg BID or TID.
- If during the titration period, the subject experiences any cardiovascular events that meet the protocol determined criteria (for detailed description see Table 2 of the Protocol), they must remain on their current dose and not be dose escalated.

[figure not shown]

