## 7.2. Interim Analysis

During Stage 1, two interim analyses are planned after 6 and 8 subjects complete the Day 14 GH assessment. The DRC will meet and review the number of GH responders on Day 14 (i.e. a GH responder is defined as a subject with GH  $\leq 2.5\mu\text{g/l}$  or with at least 50% reduction from baseline GH after 6-day titration plus 8-day treatment with BIM23B065 measured by mean serum concentration of GH over 6 hours at Day 14) as well as the safety and tolerability data defined in the DRC charter.

Based on the safety and efficacy data of these subjects, the DRC will decide if the BID cohort may be continued or stopped, and if stopped, if a TID cohort (Stage 2) may be initiated, according to the following criteria (please see

Figure 2 below).

- If there are less than 3 out of 6 (3/6) responders then the BID regimen (Stage 1) will be stopped for futility and Stage 2 will be initiated, where new enrolled subjects will follow the TID administration part (Option 1 in Figure 2).

If there is at least 3/6 responders, then the Stage 1 will continue: the next 2 subjects will follow the BID administration part and DRC will review the safety and efficacy data once 8 evaluable subjects will have completed Stage 1.

- If there are less than 4 responders (out of 8 subjects) then the BID regimen (Stage 1) will be stopped for futility and Stage 2 will be initiated, where new enrolled subjects will follow the TID administration part (Option 2 in Figure 2).

If there are at least 4 responders (out of 8 subjects), then the Stage 1 will continue: the next 4 subjects will follow the BID administration part and DRC will review the safety and efficacy data once 12 subjects will have completed Stage 1.

- If there are less than 8 responders (out of 12 subjects) then the Stage 2 will be initiated, where new enrolled subjects will follow the TID administration part (Option 3 in Figure 2).

If there are at least 8/12 responders, then no new subjects will be enrolled into the BID administration part, no TID administration part will be conducted and the study will be stopped as the primary objective is met with the BID regimen.

At any time during Stage 1 if at least 3 subjects experienced at least one dose limiting toxicity (DLT) (the definition of DLT can be found in the study protocol Table 3.) then the DRC will stop the recruitment and no TID administration part will be conducted.

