### **8. SAMPLE SIZE DETERMINATION**

A sufficient number of subject will be enrolled so that there is a maximum of 24 evaluable subjects for the primary analysis (12 per stage). Enrolled subjects who drop out of the study prior to Day 14 GH evaluation may be replaced so that 12 are evaluable per Stage. (Replacement strategy is detailed in Section 10.1.).

A minimum of 8 of the 12 evaluable subjects must be responsive to a single test dose of octreotide pre-study defined as a >50% reduction in GH.

Per the primary endpoint, a subject is defined as a responder if the mean concentration of GH over 6 hours is  $\leq 2.5\mu\text{g/l}$  or if there is at least 50% reduction from mean baseline in GH at Day 14 (after 6 days titration plus 8 days treatment).

Based on the exact test for single proportion, twelve evaluable subjects per stage would be sufficient to have over 84% power, at a significance level of 0.05 (one sided) to reject the null hypothesis that there is no indication of efficacy of BIM23B065 if the GH responder rate is at most 33%, assuming that the GH responder rate is equal to 75%.

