### 10.7. Derived and Computed Variables

The following derived and computed variables have been initially identified. It is expected that additional variables could be required. The SAP will not be amended for additional variables unless they are directly related to the primary endpoint or key secondary efficacy variables. Any additional derived or computed variables will be identified and documented in the ADaM requirement documentation and/or in the footnotes of the outputs, where appropriate.

Variable Name	Description	Valid values (Ranges)	Computation methods, Notes or equation(s)
OTPDMEN	Mean GH over 6 hours after octreotide dosing during Octreotide Test	0-200 ug/L	= [SUM(GH measurements 1, 2, 3, 4, 5, 6 hours post octreotide dose)]/number of valid GH measurements
OTRBL	Reduction from Baseline in GH level during Octreotide Test	0-100 %	= [1- (OTPDMEN/ Baseline GH level)] x 100
GHMDX	Mean GH over 6 hours measured on DayX	0-200ug/L	= [SUM(GH measurements 1, 2, 3, 4, 5, 6)]/number of valid GH measurements over 6 hours on DayX]

Protocol code: D-FR-10380-002

Protocol Title: A phase IIA, open-label, single-arm, two stage, multi-centre study to investigate the pharmacodynamics, pharmacokinetics, safety and tolerability of repeated subcutaneous administration of BIM23B065 in subjects with acromegaly

Variable Name	Description	Valid values (Ranges)	Computation methods, Notes or equation(s)
GHRGL	Reduction from Baseline in GH level on DayX	0-100 %	= [1- (GHMDX/GHM(D-1))] x 100

As a general rule mean will be calculated by summarizing the available valid (non-missing) measurements and divided by the number of measurements. Percent change from baseline will be calculated according to the following:  $[1 - (\text{present value}/\text{baseline value})] \times 100$ .

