### **13.2.1. GH responders**

The following secondary GH response criteria will be defined on Day 7 and Day 14 based on the GH profiles:

- Mean GH  $\leq$  1.0 ug/l
- Mean GH  $\leq$  2.5 ug/l
- Mean GH reduction from baseline  $\geq$  50%

The GH measurements, their mean by visit, the mean percent changes from baseline and the various GH responder criteria will be listed by patient and visit. The number and proportion (90% CI calculated by the Clopper-Pearson method) of GH responders on Day 7 and Day14 will be reported.

Descriptive summaries will be presented for the measured GH values and for the calculated percent changes from baseline. Mean (+ SE) profiles over time will be displayed graphically.

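### Does the mix of a strict and an inclusive 50% cut-off for GH response leave the primary endpoint undecided?

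*SAP*

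**What the plan says.** Section 5.2.1 defines the percentage arm of the primary endpoint strictly: ">50\%$ reduction from mean baseline GH (measured over 6 hours on Day -1". Section 6.1 repeats the strict sign in its summary of the design.

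The sections that use the definition are inclusive. Section 7.2, which tells the DRC whom to count, has "with at least 50% reduction from baseline GH after 6-day titration plus 8-day treatment with BIM23B065". Section 8, on sample size, has "or if there is at least 50% reduction from mean baseline in GH at Day 14" and presents this as the primary endpoint. Section 13.1, the primary analysis, has "or at least a 50% reduction in the mean GH change from baseline on Day 14".

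Section 10.7 supplies the quantity to be compared with the cut-off, "1- (GHMDX/GHM(D-1))] x 100", with no rounding step and no inequality.

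For the secondary GH target, Section 5.2.2 is strict (below 1.0 µg/l), while Section 13.2.1 lists "Mean GH $\leq$ 1.0 ug/l". Section 13.2.1 also lists a reduction of at least 50%, but as a secondary criterion for Days 7 and 14 and not as the composite primary endpoint.

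**The concern.** A primary endpoint should have one definition, and the endpoint section is usually taken to govern. Here the analysis section does not reproduce its sign. The responder count drives the 3/6, 4/8 and 8/12 rules and the exact test, and at these sample sizes one subject can change the outcome. The trial is open-label, so a choice of sign made after a subject had landed on the boundary would be open to criticism. Section 16, which lists departures from the protocol, does not mention GH. The wording in Section 13.1 is also loose: read literally, it speaks of a reduction in a change and not of a reduction in mean GH.

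**Working it through.** **1. Which rule operates?**

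| SAP section | Use made of the definition | Sign at 50% |
|---|---|---|
| 5.2.1 | endpoint list | strict |
| 6.1 | design summary | strict |
| 7.2 | DRC responder count | inclusive |
| 8 | sample size | inclusive |
| 13.1 | primary test | inclusive |

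All three places where responders are counted or the count is modelled agree. No responder is counted in 5.2.1 or 6.1.

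**2. The plan's own figure.** Inputs from Section 8: n = 12, null rate 0.33, alternative 0.75, one-sided 0.05. With X binomial:
- P(X ≥ 8 | 12, 0.75) = 0.1936 + 0.2581 + 0.2323 + 0.1267 + 0.0317 = 0.842, which reproduces the stated power of over 84%.
- P(X ≥ 8 | 12, 0.33) = 0.0176, and P(X ≥ 7 | 12, 0.33) = 0.0632. So 8 is the smallest count that rejects at 0.05, in line with the 8/12 rule.

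**3. Who is affected?** Only a subject whose reduction is exactly 50% and whose Day 14 mean GH is above 2.5 µg/l. At or below 2.5 the subject responds through the other arm. An exact halving to more than 2.5 requires a baseline mean above 2 × 2.5 = 5 µg/l.

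**4. How often does that happen?** The SAP gives no GH distribution, so this is an assumption:
- baseline median 5 to 20 µg/l, log-SD 0.8;
- Day 14 to baseline ratio with median 0.4, log-SD 0.6;
- six samples with CV 30%, GH recorded to one or two decimals;
- 1,000,000 simulated subjects per case.

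On unrounded reductions the per-subject probability d of such a tie is 0.00005 to 0.0007. The chance of any tie among 12 is 1 − (1 − d)^12, which is 0.06% to 0.84%.

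**5. Effect on the Stage 1 decision.** Each subject is a clear responder (probability π − d), a tie (d) or a non-responder (1 − π), where π is the inclusive rate. All outcomes were enumerated through the 6, 8 and 12 looks, counting any difference in where or how Stage 1 ends:

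| True rate π | d = 0.00005 | d = 0.0007 |
|---|---|---|
| 0.75 | 0.01% | 0.17% |
| 0.60 | 0.02% | 0.31% |

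**6. Effect on power.** With the strict sign the alternative becomes 0.75 − d. At d = 0.0007, P(X ≥ 8 | 12, 0.7493) = 0.841, still over 84%.

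**7. Secondary target.** A mean GH of exactly 1.0 µg/l is the only value on which Sections 5.2.2 and 13.2.1 differ. The result is a proportion with a 90% interval; it has no test and no stopping rule.

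**The case for a change.** The strongest case for acting is the cliff at the decision boundary. With 8/12 the exact p-value is 0.0176 and the lower 90% limit is 39.1%: the null is rejected and the study stops with its objective met on BID. With 7/12 they are 0.0632 and 31.5%: the null stands and a TID cohort opens. One reclassified subject could separate the two, and the SAP sets no rounding rule. If reductions were rounded to whole percentages before classification, d would rise to 0.006 to 0.0115. The chance of any tie among 12 would be about 7% to 13%, and the Stage 1 decision would differ in about 1.5% to 5% of trials.

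The cliff is real, but it belongs to any rule with 12 subjects and does not depend on the sign. Whole-percent rounding is not a step in the plan: Section 10.7 gives a ratio formula, and analysts would apply the cut-off to the computed value. The upper ends of both ranges (0.3% and 5%) also use a true rate of 60%, whereas the assumed model itself implies responder rates of about 65% to 76%. The worry about choosing a sign after seeing data carries little weight, because the DRC rule and the primary analysis already state it, and in the same way.

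The loose phrase in Section 13.1 is settled by the Section 10.7 formula. What stands is that two descriptive sections carry a different sign from the three that do the counting, and that the 1.0 µg/l target has the same blemish.

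**Conclusion.** This is a clerical inconsistency with no practical consequence, and it calls for no change to the plan. The DRC rule, the sample size and the primary analysis share one inclusive definition, so following the SAP as written gives a single result. Only an exact tie would be classified differently under the strict sign. That alters a Stage 1 decision in roughly 0.01% to 0.3% of trials, and 0.01% to 0.17% at the planning rate of 75%. Sample size, the 8/12 threshold and the stated power are untouched. The tie probabilities rest on an assumed GH distribution and on classification of unrounded values; the agreement among Sections 7.2, 8 and 13.1 rests on the text alone. The protocol is not at hand, so which sign it carries was not checked.

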During Stage 2, two interim analyses are planned after the first 6 and 8 subjects will have completed the GH Day 14 assessment. The DRC will review safety and efficacy data of these subjects in order to decide if the trial may be stopped early for futility or not (please see Figure below).

**Protocol code:** D-FR-10380-002

**Protocol Title:** A phase IIA, open-label, single-arm, two stage, multi-centre study to investigate the pharmacodynamics, pharmacokinetics, safety and tolerability of repeated subcutaneous administration of BIM23B065 in subjects with acromegaly

If there are less than 3/6 responders, then no new subjects will be enrolled into the TID administration part and the study will stop (Option 1 in Figure ).

If there are at least 3 responders (out of 6 subjects), then the next 2 subjects will follow the TID administration part and DRC will review the safety and efficacy data once 8 subjects will have completed Stage 2.

If there are less than 4 responders (out of 8 subjects) then the TID regimen (Stage 2) will be stopped for futility, no new subjects will be enrolled into the TID administration part and the study will stop (Option 2 in Figure ).

If there are at least 4 responders, then Stage 2 will continue: the next 4 subjects will follow the TID administration part once 12 subjects will have completed Stage 2 and the study will be stopped (Option 3 in Figure ).

Again, at any time during Stage 2 if at least 3 subjects experienced at least one DLT, then the DRC will stop the recruitment.

Figure 2 BID administration part (Stage 1)

[figure not shown]
[figure not shown]

Figure 3 TID administration part (Stage 2)

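### Minor: Section 8's power and Section 13.1's 90% interval and p-value are fixed-n figures that leave out the futility stops of Section 7.2; power is 83.6% if the stops bind, and no verdict against 33% changes

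*SAP*

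**What the plan says.** - SAP Section 8 bases the sample size on the exact single-proportion test, with a null rate of at most 33%, an assumed rate of 75% and a one-sided 5% level, and concludes that "twelve evaluable subjects per stage would be sufficient to have over 84% power". It does not mention the interim looks.
- SAP Section 7.2 places looks after 6 and 8 subjects in each stage. Fewer than 3 responders of 6 ends the stage, and at the second look: "If there are less than 4 responders (out of 8 subjects) then the BID regimen (Stage 1) will be stopped for futility". For Stage 2 the wording at the second look is "then the TID regimen (Stage 2) will be stopped for futility".
- The same section also uses softer wording: "the DRC will decide if the BID cohort may be continued or stopped", and for Stage 2 the committee reviews data "in order to decide if the trial may be stopped early for futility or not". Section 6.1 likewise says the arm may be terminated.
- A separate safety stop can act at any sample size: "At any time during Stage 1 if at least 3 subjects experienced at least one dose limiting toxicity (DLT" recruitment stops. Stage 2 has the same rule.
- SAP Section 13.1 reports the responder proportion, which "will be reported with its 90% confidence interval calculated using the exact Clopper-Pearson method". It adds: "The exact p-value will be reported". The null is rejected when the lower limit exceeds 33%. The looks are not mentioned.

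**The concern.** A Clopper-Pearson interval and a binomial p-value are exact for a sample size chosen in advance. Here the final n depends on the responses, so the set of possible results differs from that of 12 independent subjects followed to the end. A result such as 5/12 can only be seen if the stage had at least 3/6 and at least 4/8, and the fixed-n calculation ignores that condition. In the same way, Section 8 counts as successes some sequences that Section 7.2 would have stopped.

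The power statement and the interval reported for a regimen that narrowly fails are at stake. That interval tells a reader whether a failed regimen is still compatible with the 75% rate on which the trial was sized.

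**Working it through.** **Inputs.** n = 12, p0 = 0.33, p1 = 0.75, one-sided 0.05 (Section 8). Stop below 3/6 or below 4/8 (Section 7.2). Reject if the lower 90% Clopper-Pearson limit exceeds 33% (Section 13.1).

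**1. The plan's own figure.** At n = 12 and p = 0.33, P(X ≥ 7) = 0.0632 and P(X ≥ 8) = 0.0176, so the critical count is 8. P(X ≥ 8 | 0.75) = 0.8424. The stated power of over 84% reproduces for a fixed n.

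**2. Power with binding stops.** A success is lost only if a stopped path could still have reached 8/12.
- From 0/6 or 1/6 the maximum is 7/12; from 3/8 it is also 7/12. Nothing is lost there.
- From 2/6, six responders in the remaining six give 8/12. At 75%: P(2/6) = 15 × 0.75² × 0.25⁴ = 0.03296 and P(6/6) = 0.75⁶ = 0.17798, with product 0.00587.
- Power = 0.84236 − 0.00587 = 0.83649, or 83.6%.
- Type I error at 33%: P(2/6) × P(6/6) = 0.32917 × 0.00129 = 0.00043, so 0.01760 − 0.00043 = 0.01717, or 1.7%.
- If the stops are advisory, power lies between 83.6% and 84.2%, depending on how often a stop at 2/6 is overridden.

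**3. Why the interval moves: 5/12 as the example.** With the stage-wise ordering 0/6 < 1/6 < 2/6 < 3/8 < 4/12 < ... < 12/12, the upper limit is the p at which the probability of 5/12 or anything lower equals 0.05. At p = 0.75 this is 0.0376 (stopped at 6) + 0.0082 (stopped at 8) + 0.0003 (4/12) + 0.0040 (5/12) = 0.0501, so the limit is 75.0%. At fixed n the same tail is P(X ≤ 5) = 0.0143, and the planned upper limit is 68.5%.

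The p-value at 33% for 5/12 is 1 − 0.6870 − 0.0970 − 0.0265 = 0.190 with the stops, against 0.359 at fixed n.

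**4. All affected results** (90% limits in %, p-value against 33%):

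| Result | Planned limits | Stage-wise limits | p planned | p with stops |
|---|---|---|---|---|
| 3/8 | 11.1-71.1 | 15.3-74.4 | 0.524 | 0.313 |
| 4/12 | 12.3-60.9 | 20.5-74.4 | 0.597 | 0.216 |
| 5/12 | 18.1-68.5 | 22.5-75.0 | 0.359 | 0.190 |
| 6/12 | 24.5-75.5 | 26.6-77.5 | 0.171 | 0.124 |
| 7/12 | 31.5-81.9 | 32.3-82.2 | 0.063 | 0.056 |
| 8/12 | 39.1-87.7 | 39.2-87.7 | 0.018 | 0.017 |

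Stage-wise limits equal the planned ones for 0/6, 1/6, 2/6 and from 9/12 up. From 5/12 upward, ordering by observed rate gives the same limits. Below that the ordering matters. By observed rate, 3/8 has 16.4-74.4%, and 4/12 has 15.3-72.9% if ranked above 2/6 or 6.3-72.9% if tied with it.

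**5. How likely these results are.** At a true rate of 33%, 3/8 or 4/12 has probability 12.4%, and 5/12 or 6/12 has 13.3%. At 50% the figures are 9.2% and 20.9%; at 75%, 0.9% and 2.9%.

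**6. Coverage of the planned interval under binding stops.** It is 98.3% at a true rate of 33%, 96.5% at 50% and 91.8% at 75%. It falls below 90% only for true rates of about 75.5-76.4%, with a minimum of 89.6%. Upper-side error reaches 7.0%; lower-side error stays at or below 5.0%.

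**The case against.** The strongest defence is that Section 8 names the test and sample size behind its figure, and for that test the figure is right. The looks allow stopping for futility only, never an early efficacy claim, so ignoring them in the final test is a recognised conservative choice: type I error falls from 1.76% to 1.72%. Section 6.1 and part of Section 7.2 say may rather than will, and if the rules are guidance the fixed-n power is the usual one to quote. A design-adjusted interval in a 12-subject phase IIA stage could also be called a matter of taste.

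Most of this stands, and it is why the point is minor. It does not cover the upper limit, which the stops make too low rather than conservative. Nor does the SAP say that it chose to ignore the looks, or whether they bind.

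Two stronger readings are tempting. A reader might infer that Section 8 miscalculates its power or that the primary conclusion is at risk. Neither follows: the figure reproduces, and all 13 possible final results keep the same verdict against 33%.

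A reader might also infer that the lower limit and p-value are conservative in every case. That was checked only for stops at 6, 8 and 12. A DLT stop can end a stage at another n, where 3/3, 4/5 or 5/7 already puts the lower limit above 33%. If such stops could fall after any subject from the third to the twelfth, in the least favourable relation to response, the error at 33% could reach 9.4%. That is an extreme bound, not an expected value, but it rules out an unconditional assurance.

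**Conclusion.** The point holds as a minor one. If the stops of Section 7.2 bind, power per stage at 75% is 83.6%, narrowly short of the stated level, and the loss of 0.6 point comes entirely from the look at 6. The planned interval and p-value are fixed-n quantities. Under the stops they differ for 3/8 and for 4/12 to 6/12, and slightly at 7/12. The largest shift under the stage-wise ordering is at 4/12, where the upper limit rises by 13.5 points (60.9% to 74.4%), but the limits for 4/12 and 3/8 depend on the ordering. The clearest case is 5/12, where both orderings agree: the planned interval excludes 75%, while the one that respects the stops just reaches it.

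The 8/12 criterion stands. These results assume independent responses, a common response rate within a stage, looks exactly at 6, 8 and 12, and no stop overridden. The success count of 8 is stated in Section 7.2 for Stage 1; for Stage 2 it follows from the test in Section 13.1.

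**What to change.** **Section 8.** State that power per stage at a true rate of 75% is 83.6% with the futility rules of Section 7.2 applied (one-sided type I error 1.7% at 33%), and 84.2% if they are not applied.

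**Section 13.1.** Keep the decision rule, the p-value and the Clopper-Pearson interval, and add:
- The interval and p-value do not account for the futility looks.
- When the 6/8/12 looks were followed, the lower limit and the p-value remain conservative, but the upper limit does not. In that case the exact 90% interval under the stage-wise ordering (0/6 < 1/6 < 2/6 < 3/8 < 4/12 < ... < 12/12) is given per stage as a supportive line.
- For any other stopping pattern or analysed n (a stop overridden, a DLT stop, unreplaced withdrawals, exclusions from the Efficacy Evaluable population), only Clopper-Pearson is given, labelled as a fixed-n interval and with no claim that it is conservative.

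The stage-wise ordering is named in advance because ordering by observed rate ties 2/6 with 4/12 and would need a tie rule.

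The cost is a few sentences, one short enumeration program and a slightly lower stated power. Design, sample size and decision rule stay as they are. The supportive line will be unavailable whenever the analysed n is not 6, 8 or 12, which limits its use but not its correctness.
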